7.7 Safety Analyses

No inferential statistics are planned for any safety assessment.

7.7.1 *Adverse Events*

Safety assessments will be based mainly on the nature, frequency, relationship, and severity of adverse events (AEs). AEs will be coded by primary system organ class (SOC) and preferred term (PT) according to the Medical Dictionary for Regulatory Activities (MedDRA) version 22.0. The treatment-emergent adverse events (TEAEs) will be summarized by the number and percentage (n and %) of subjects in each SOC and PT. For summaries by relationship to study drug, “possibly related” will be combined with “related”, and “unlikely/remote related” will be combined with “not related.” When multiple AEs are reported with the same preferred term, the AE of the strongest relation will be included in the summary by relationship, and the AE of the most severe grade will be included in the summary by severity table.

The following AE incidence tables will be presented.

- Overview of TEAEs to include

- Number (%) of subjects who reported at least one TEAE
- Number (%) of subjects who reported at least one treatment-related TEAE
- Number (%) of subjects who reported at least one severe TEAE
- Number (%) of subjects who reported at least one serious TEAE
- Number (%) of subjects who reported at least one TEAE leading to treatment discontinuation
- TEAEs by PT sorted by decreasing order of subject incidence in the combined dose groups
- TEAEs by SOC and PT sorted alphabetically
- Study Drug-Related TEAEs by SOC and PT
- TEAEs with Grade 2+ Severity by SOC and PT

All AEs will be listed with onset/stop day, relationship to study drug, severity, action taken, and outcome. Pertinent subject information including dose group and demographics will also be included. Separate listings will be provided for TEAEs leading to study discontinuation, treatment-emergent serious AEs (TESAEs), and infusion-related TEAEs.

7.7.2 *Laboratory Test*

Hematology, biochemistry, and urinalysis test results will be summarized by dose group and visit using descriptive statistics. For quantitative laboratory parameters, both actual values and change from baseline values will be summarized.

Laboratory test result will be classified as low, normal, high (LNH) according to whether the value is below (L), within (N), or above (H) the reference range provided by the laboratory. Within-treatment comparisons for hematology and chemistry will be based on the 3x3 shift tables that, for a particular laboratory test, showing how the LNH classification at baseline shifts to the LNH classification at postbaseline visit.

A complete lab data listing, including hematology, biochemistry, and urinalysis will be provided for all subjects.

7.7.3 *Vital Signs*

Vitals signs are resting pulse (beats per minute), oral body temperature (°C), systolic blood pressure (mmHg), and diastolic blood pressure (mmHg). Vital signs will be summarized by dose group at each scheduled timepoint. Summaries will present both actual and change-from-baseline results.

7.7.4 *ECG*

The investigator evaluation for the overall ECG findings by normal, abnormal not clinically significant (NCS), and abnormal clinically significant (CS) will be tabulated with number and % of subjects at each time point.

Actual and change from baseline in PR, QRS, QT, RR, QTc, and HR will be summarized with descriptive statistics at each time point.

Data listings will be presented for ECG parameters by time point. QTc meeting the criteria of >450 but ≤480, >480 but ≤500 or >500 msec for the actual value, or >30 msec or >60 msec increase from baseline will be identified.

7.8 Pharmacokinetic Analysis

7.8.1 Sample collections for Pharmacokinetic Analysis

Blood samples will be obtained for PK analysis at baseline, before dosing and again at 1, 2, 3, 4, 6, 8, 12, 18, and 24 hours post-dosing.

7.8.2 Pharmacokinetic Parameter Calculation Methods

Pharmacokinetic parameters will be calculated by the noncompartmental analysis method from concentration-time data following these guidelines:

- Actual sampling times relative to the start time of the study drug infusion will be used for all calculations of the PK parameters. If the actual time is not available, the scheduled time will be used.
- Concentrations from unscheduled PK blood samples will be used in the derivation of the parameters.
- There will be no imputation of missing data.

For the calculation of the non-compartmental parameters,

- Pre-dose concentration $\geq 5\%$ of the corresponding C_{max} will be excluded from analysis.
- Concentration below the lower limit of quantification (LLOQ) occurring from the predose to the first concentration $\geq LLOQ$ will be set to zero.
- All remaining concentration below LLOQ (BLOQ) will be set to missing.

Pharmacokinetic parameters will be estimated according to the following guidelines:

- The maximum observed plasma concentration (C_{max}) will be obtained directly from the concentration-time data.
- Time to maximum concentration (T_{max}) is the time at which C_{max} is observed.
- The apparent terminal elimination rate constant (λ_z) will be estimated at terminal phase by linear regression after log-transformation of the concentrations:
 - Only those data points that are judged to describe the terminal log-linear decline will be used in the regression.
 - A minimum number of three data points in the terminal phase will be used in calculating λ_z with the line of regression starting at post- C_{max} data point (C_{max} will not be part of the regression slope) and including C_{last} and t_{last} .
 - The adjusted correlation coefficient (R^2 adjusted) in general should be greater than 0.90. Any value less than 0.90 may be used according to the pharmacokineticist's best knowledge and judgment.
 - An appropriate number of decimal places should be used for λ_z to enable the reported value of half-life ($t_{1/2}$) to be calculated.
- Half-life ($t_{1/2}$) will be calculated as $\text{Log}_e(2)/\lambda_z$.

- AUC will be calculated as follows:
 - The linear trapezoidal method will be employed for all incremental trapezoids arising from increasing concentrations and the logarithmic trapezoidal method will be used for those arising from decreasing concentrations.
 - $AUC_{(0-t)} = \int_0^t C(t)dt$
 - $AUC_{(0-\infty)} = \int_0^t C(t)dt + \int_t^{\infty} C(t)dt = AUC_{(0-t)} + C_t / \lambda_z$
- C_t is the last observed quantifiable concentration.
- Volume of distribution (V_d) will be estimated based on the terminal phase as Dose/($\lambda_z \cdot AUC_{0-\infty}$).
- Apparent clearance CL will be estimated as Dose/AUC_{0-∞}.

7.8.3 *Pharmacokinetic Concentrations and Variables*

The analysis of the PK data will be based on the PK analysis set.

Concentrations will be listed by dose group, subject, nominal time, and actual time. Concentrations that are below LLOQ will be indicated by BLOQ in this listing.

Concentrations will be summarized by dose group at each time point. The following descriptive statistics will be presented at each nominal time point: n, arithmetic mean, SD, geometric mean, %CV, median, minimum and maximum.

PK parameters will be summarized. Descriptive statistics for calculated PK parameters will include: n, arithmetic mean, SD, geometric mean, %CV, median, minimum and maximum values. The geometric mean and %CV will not be presented for T_{max} . Values of %AUC extrapolated > 20% will be flagged in the listings.

Individual plasma concentration versus actual times will be plotted by dose in linear and semi-logarithmic scale. Mean plasma concentration at the scheduled timepoints will be plotted by dose group in linear and semi-logarithmic scale with the associated standard errors (SE only for the linear scale) at each scheduled timepoint.

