# 11.5 Analysis of Pharmacokinetic (PK) Data

Pharmacokinetic (PK) parameters will be calculated for each subject and summarized by treatment group. PK profiles in which the pre-dose concentration is > 5% of the corresponding  $C_{max}$  (and therefore greater than the lower limit of quantification [LLOQ]) will be excluded from all descriptive statistics and statistical analyses.

For the PK analysis performed, actual blood sampling times will be used in all PK analyses. Protocol-specified times will be used to calculate mean plasma or serum concentrations for

Protocol Number: REN-003 (Original)

Date: 25 March 2019

tabular and graphical displays. All PK calculations and generation of individual subject plasma or serum concentration versus time graphs will be performed using SAS®.

PK parameters will be calculated using non-compartmental analysis. The maximum serum concentration ( $C_{max}$ ) and time to maximum serum concentration ( $T_{max}$ ) will be obtained directly from the data. The elimination rate constant ( $\lambda z$ ), elimination half-life ( $T_{1/2}$ ), area under the concentration-time curve from time 0 to time t ( $AUC_{[0-inf]}$ ) and area under the concentration-time curve from time 0 to infinity ( $AUC_{[0-inf]}$ ), clearance (CL), and volume of distribution (Vz) will be calculated for each subject and summarized by treatment group. Only plasma samples with concentrations  $\geq LLOQ$  will be used in the PK analysis. Plasma concentrations  $\leq LLOQ$  will be taken as 0 for the calculation of the descriptive statistics at each sampling time. For the PK analysis, plasma concentrations  $\leq LLOQ$  that occur from pre-dose to the first concentration  $\geq LLOQ$  will be taken as 0 and those that occur thereafter will be taken as missing.

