1 INTRODUCTION

This is a Phase 1b single-center, dose-escalating study to evaluate the safety, tolerability, PK and pharmacodynamic effect of SnPP in healthy volunteers and in subjects with stage 3-4 CKD. The following biomarkers will be used as surrogate measures of cytoprotective activity: Haptoglobin, Ferritin, Bilirubin, Hemopexin, IL-10, and Heme Oxygenase-1. Additionally, the P21 biomarker will be monitored at various points of the study as well as urine biomarker response to SnPP.

The purpose of this statistical analysis plan (SAP) is to specifying the statistical approaches for the data analysis prior to database lock. This SAP covers the planned analyses of all data collected on the electronic case report forms (eCRFs). This SAP supersedes the statistical methods described in the clinical protocol. Deviations/changes from the planned analyses described in this SAP will be identified, with justification, in the appropriate section of the clinical study report. This SAP is developed based on the clinical study protocol REN-003, dated 29 March 2019.

The reader of this SAP is encouraged to also read the clinical protocol and other related documents for details on the planned conduct of this study. Operational aspects related to the collection and timing of planned clinical assessments are not repeated in this SAP unless relevant to the planned analyses.

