6 ANALYSIS POPULATIONS

The **Safety Analysis Population** will include all subjects who received study medication. This population will be used for all demographics, baseline characteristics, and safety summaries.

The **Modified Intent-to-Treat (MITT) Population** will include all subjects who received study medication and have a post-baseline efficacy assessment. This population will be used for all efficacy analysis.

The **PK Analysis Population** will include all subjects who receive study medication and provided sufficient and valid serum SnPP concentration data to allow the determination of PK parameters. This population will be used for the PK parameter summaries.

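### SAP 7.8.2 narrows the protocol's pre-dose PK rule from excluding the whole profile to excluding one concentration, and the two documents use different inequalities

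*SAP*

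**What the plan says.** Protocol 11.5 makes the profile the thing excluded: "PK profiles in which the pre-dose concentration is > 5% of the corresponding" Cmax "will be excluded from all descriptive statistics and statistical analyses".

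SAP 7.8.2 makes the concentration the thing excluded: a pre-dose concentration at or above 5% "of the corresponding C_{max} will be excluded from analysis". The bullet stands under the lead-in "For the calculation of the non-compartmental parameters". The two bullets after it also deal with single concentrations: values below the LLOQ are set to zero up to the first quantifiable one and to missing afterwards. The same section states: "There will be no imputation of missing data".

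On precedence, SAP section 1 states: "This SAP supersedes the statistical methods described in the clinical protocol". SAP Amendment 1 changes only the definition of baseline and the tables that depend on it, so the PK rule stands as written.

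The SAP's PK Analysis Population (section 6) takes treated subjects who "provided sufficient and valid serum SnPP concentration data to allow the determination of PK parameters". It gives no criterion based on the pre-dose value.

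**The concern.** Both documents react to the same warning sign at about 5% of Cmax but act on different objects, and an analyst cannot follow both. Under the protocol, an affected profile contributes nothing and that dose group falls from 6 to 5. Under the SAP's literal wording the group stays at 6, and the profile's Cmax, AUC, half-life, clearance and volume remain in the summaries.

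A measurable pre-dose SnPP level before a single dose points to assay background, a sample mix-up or earlier exposure. In the first and third cases the later samples carry the same signal, so removing the time-0 value does not clean the profile. A fixed background would be the largest share of Cmax at the lowest dose. PK is one of the study's four primary objectives and the cohorts have 6 subjects, so a single retained profile is visible in a cohort mean.

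The SAP also leaves a gap. If the pre-dose value is dropped and nothing is imputed, it does not say how the first interval of AUC(0-t) is to be computed.

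**Working it through.** The plan gives no figure to reproduce, so the check has two parts: the texts side by side, and an illustration of what deleting one value does.

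**Texts**

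| | Protocol 11.5 | SAP 7.8.2 |
|---|---|---|
| Object excluded | the PK profile | the pre-dose concentration |
| Threshold | > 5% of Cmax | ≥ 5% of Cmax |
| Excluded from | all descriptive statistics and analyses | analysis, within the non-compartmental calculation |
| Rest of the profile | out | no rule |

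The inequality differs only for a value of exactly 5%. The object excluded is the substantive difference.

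**Illustration**

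Inputs from the documents:
- infusion over 2 h (protocol 9.5.4)
- samples at 0, 1, 2, 3, 4, 6, 8, 12, 18 and 24 h (protocol 9.3)
- linear-up/log-down AUC, with AUC(0-inf) = AUC(0-t) + C_t/λz (SAP 7.8.2)
- 6 subjects per group (SAP 3)

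Assumptions, not in the documents:
- one-compartment decline with a true half-life of 4, 8 or 12 h
- pre-dose value p = 5% or 10% of observed Cmax
- λz from the 12, 18 and 24 h points
- the deleted time-0 value treated as 0

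*Case A, constant background.* Scale the true Cmax to 100. The observed curve is C(t) + B, with B = 100·p/(100 − p), so B = 5.26 for p = 5 and 11.11 for p = 10.

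Worked example, half-life 4 h and p = 10:
- True: AUC(0-t) = 668.6; C(24) = 2.21; λz = ln 2/4 = 0.1733. AUC(0-inf) = 668.6 + 2.21/0.1733 = 681.4.
- Observed with the pre-dose value deleted: AUC(0-t) = 935.9; C(24) = 13.32; fitted λz = 0.0642. The tail is about 207.4, so AUC(0-inf) is about 1143.3.
- Ratio 1143.3/681.4 = 1.678. Half-life reads ln 2/0.0642 = 10.8 h. CL changes by 1/1.678 − 1 = −40%.

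| True half-life | p | AUC(0-inf) ratio, value kept | AUC(0-inf) ratio, value deleted | CL | Half-life reads |
|---|---|---|---|---|---|
| 4 h | 5% | 1.290 | 1.286 | −22% | 7.4 h |
| 8 h | 5% | 1.190 | 1.188 | −16% | 9.7 h |
| 12 h | 5% | 1.161 | 1.160 | −14% | 13.6 h |
| 4 h | 10% | 1.686 | 1.678 | −40% | 10.8 h |
| 8 h | 10% | 1.424 | 1.420 | −30% | 11.6 h |
| 12 h | 10% | 1.356 | 1.353 | −26% | 15.4 h |

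Deleting the value changes the ratio by less than 0.01 in every row. Starting the AUC at 1 h instead of treating time 0 as 0 removes a little more: at 4 h and 5%, the AUC(0-t) ratio is 1.146 rather than 1.191. The inflation remains.

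If the six subjects have equal true AUC, one affected profile moves the cohort mean by 16%/6 ≈ 3% up to 68%/6 ≈ 11%.

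*Case B, carry-over decaying at the drug's own half-life.* The observed curve is C(t) + b·exp(−λz·t), with b chosen so that the pre-dose value is p% of observed Cmax. With the value deleted, AUC(0-inf) ratios at 4, 8 and 12 h are 1.040, 1.046 and 1.048 for p = 5, and 1.083, 1.096 and 1.101 for p = 10. The fitted half-life is unchanged. One such profile moves the cohort mean by 4%/6 ≈ 0.7% up to 10%/6 ≈ 1.7%.

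*Case C, only the pre-dose sample is faulty.* All later values are correct. Over half-lives of 3-10 h and a false pre-dose value of 5-20% of Cmax, keeping the false value shifts AUC(0-t) by 0.2-1.9%. Deleting it and starting at 1 h loses 2-5%.

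**The case against.** The strongest reply is that this is loose drafting with little reach. The SAP bullet may be a careless shortening of the protocol's rule, since the LLOQ bullets beside it follow the protocol closely. The SAP never says that the remaining profile is kept. Its PK population requires valid data, and reasons for exclusion from that set are to be listed, so a route to drop a profile exists. There is no earlier study dose to carry over, recent use of investigational drugs is an exclusion criterion, and the SAP's PK output is descriptive. This stands as far as frequency and severity go. It does not settle the rule, because no pre-dose criterion is written into the PK population and the literal SAP text governs.

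A reader might infer more than the documents support:

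- *That the SAP reverses the protocol's rule.* It does not. Both exclude at about 5% of Cmax, and the SAP narrows what is excluded.
- *That the SAP hides the contamination.* The bullet is confined to the parameter calculation. SAP 7.8.3 lists concentrations for each subject by time and plots individual profiles, so the pre-dose value remains visible.
- *That dose escalation is affected.* The escalation rules stand in protocol 11.5, beside the protocol's own whole-profile rule, and SAP 7.8 contains none. Nothing shows that the SAP bullet governs those reviews. For the first step, which uses the cohort maximum, an inflated profile would overstate exposure, which is the cautious direction. The effect on the later power model could go either way.
- *That every affected profile is badly biased.* Case A is one of three possible causes. In Case B the bias is modest, and in Case C the whole-profile rule discards a sound profile.

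**Conclusion.** The documents conflict on what is excluded and, trivially, on the inequality. The SAP's wording is the weaker safeguard when the pre-dose signal persists into later samples. AUC(0-inf) then stays about 16-68% too high under an assumed constant background of 5-10% of Cmax with a true half-life of 4-12 h, and about 4-10% too high with half-life unchanged if the signal is carry-over decaying at the drug's own rate. If only the pre-dose sample is at fault, no such bias arises. The half-lives, the background levels and the one-compartment shape are assumptions; the documents give none of them. The event should be rare and an effect on escalation is not established. Severity is minor: a wording conflict to resolve before the PK parameters are finalised.

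**What to change.** Replace the SAP 7.8.2 bullet with the protocol's rule, for example: if a subject's pre-dose concentration is > 5% of that subject's Cmax, the whole profile is left out of the PK parameter summaries and statistical analyses and is listed with the reason. Use > 5% in both documents. Since the protocol's exclusion covers all descriptive statistics, say also whether the time-point concentration summaries in SAP 7.8.3 omit the profile. If the sponsor does intend to drop only the single value, the SAP should say so, justify the departure from the protocol, and state how time 0 enters the AUC.

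The cost is one sentence in the SAP. The downside is the loss of an affected subject from a cohort of 6, including in the case where only the pre-dose sample was faulty. The protocol already accepts that loss.

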7.9 Interim Analysis

No interim analyses are planned for this study.

8 SAMPLE SIZE CALCULATIONS

No formal sample size calculation has been performed for the study. However, it is believed that 6 subjects per dose group will be adequate to establish differences in biomarker response between groups.

9 REFERENCES

10 TIME AND EVENTS SCHEDULE OF STUDY PROCEDURES

10.1 Event Schedule – All subjects

Study Day	Screening	1	2,3,4,5,8 ¹	14 ^{**}	29/End of Study ¹
Parameter	Within 14 days prior to first dose				
Written informed consent	X				
Eligibility criteria	X				
Demographics	X				
Medical history	X				
Physical examination and weight	X	X ²			X
Electrocardiogram	X	X ^{2,3}			X
Vital signs	X	X ²	X		X
Serum chemistry ^{8,9}	X	X ²	X		X
Hematology ^{8,9}	X	X ²	X		X
Baseline determination ¹³	X	X			
Response biomarkers ^{8,11}		X ^{2,4}	X		
Safety biomarkers ^{8,12}		X ²	X	X	X
SnPP PK ^{4,11}		X			
Urinalysis including sediment ⁹	X	X ²	X		X
Urine pregnancy test ¹⁰	X	X	X at Day 8		X
Urine drug/alcohol/cotinine screen	X				
Confinement in clinical testing unit ⁵		X ⁵			
SnPP infusion		X ⁶			
Discharge from clinical testing unit			X ⁷		
Prior/Concomitant medications	X	X	X		X
Adverse events		X	X		X
Investigational product reconciliation					X

¹ Day 8 visit will occur (± 1) days and End of Study (EOS) visit will occur 28 (± 1) days after administration of SnPP.

² Baseline parameters performed prior to dosing on Study Day 1.

³ Two ECG's will be performed on Study Day 1: the first at Baseline (prior to infusion) and the second within 10 minutes of infusion completion.

⁴ Blood samples for SnPP pharmacokinetic analysis will be assessed at baseline and 1, 2, 3, 4, 6, 8, 12, 18, and 24, hours (± 15 minutes) after start of infusion. Additional biomarker samples will also be collected at 2, 4, 8, 12, 18 hours (± 15 minutes) after start of SnPP. Urinary tin excretion will be measured on a 24-hour urine sample.

⁵ Subjects will be confined in the clinical testing unit a minimum of 24 hours from the morning of Study Day 1 until after collection of the 24-hour post-dose sample on Study Day 2.

⁶ SnPP will be administered by infusion over 120-minutes after Baseline ECG, vital signs and blood and urine samples are collected.

⁷ Discharge from unit following evaluations and sample collection required on Study Day 2

⁸ Measured fasting (nothing by mouth except water, coffee or tea, with or without milk and/or sugar, and essential medications only for a minimum of 8 hours prior to sample collection at the clinic).

⁹ Parameters to be measured are detailed in Appendix 1.

¹⁰ For women of childbearing potential using kits supplied by the laboratory

¹¹ Haptoglobin, Ferritin, Bilirubin, Hemopexin, IL-10, P21 and HO-1.

¹² Cystatin-C, IL-6, SnPP, total porphyrin, Tin, Troponin I, albuminuria, Kidney Injury Molecule-1 (KIM-1), Neutrophil Gelatinase-Associated Lipocalin (NGAL), N acetyl-beta-D-glucosaminidase (NAG), (in addition to BUN/Cr which are part of the Serum Chemistry panel)

¹³ Three measurements will be taken for the urinary safety biomarkers (albuminuria, Kidney Injury Molecule-1 (KIM-1), Neutrophil Gelatinase-Associated Lipocalin (NGAL), and N acetyl-beta-D-glucosaminidase (NAG)), eGFR, and response biomarkers prior to dosing.

** Day 14 safety evaluation will be conducted at the request of the DSMB after each cohort safety review

11 CONVENTIONS FOR THE PRESENTATIONS OF TABLES, FIGURES AND LISTINGS

The specification for the tables, Figures and Listings are provided in a separate document.

